9.4.5 Selection and Timing of Dose for Each Subject

Elenbecestat (E2609) is administered orally, QD, in the morning with or without food. Study treatment will begin on Day 1 following randomization and will continue for 24 months.

9.4.6 Blinding

Elenbecestat (E2609) and placebo will be administered as tablets of identical appearance.

During the Randomization and Follow-Up Phases, subjects and all personnel involved with the conduct and interpretation of the study, including investigators, site personnel, and sponsor staff will be blinded to the treatment codes (double-blind). Randomization data will be kept strictly confidential, filed securely by an appropriate group with the sponsor or CRO, and accessible only to authorized persons (eg, Eisai Global Safety) until the time of unblinding, per the standard operating procedure.

PK and PD data will be provided to the sponsor by the PK and PD analysis laboratories using dummy subject numbers instead of actual subject numbers. The same dummy subject number will be used for a subject's PK and PD data. These data will be used to evaluate whether the PK and PD effects seen in this study are similar to those seen in previous studies. Thereafter, unblinded PK and PD data will only be provided to the sponsor after study completion.

In the event that emergency conditions require knowledge of the study treatment given, the blind may be broken via the code breaker facility within the IxRS. Emergency procedures for revealing drug codes are given in [Section 9.5.4.5](#). If possible, before breaking the blind, the investigator should consult with the sponsor to ascertain the necessity of breaking the code. If an AE results in the investigator breaking the blind, then that AE must be reported as a SAE.

9.4.7 Prior and Concomitant Therapy

Any medication (including over-the-counter medications) or therapy administered to the subject prior to the study (within 6 months of randomization) and during the study (starting at the date of informed consent) will be recorded on the Prior & Concomitant Medication eCRF or Non-Pharmacological Procedures eCRF. The investigator will record on the Adverse Event eCRF any AE for which the concomitant medication/therapy was administered. If the concomitant medication/therapy is being administered for a medical condition present at the time of entry into the study, the investigator will record the medical condition on the Medical History and Current Medical Condition eCRF.

Listings of prohibited and permitted drugs are provided in [Appendix 2](#) (Prohibited medications are presented in [Listing 1](#), [Listing 2](#), and [Listing 3](#). Medications that are permitted with restrictions are listed in [Listing 4](#), [Listing 5](#), and [Listing 6](#)).

The following agents are not permitted before randomization (specific time frames are shown below) and until the last visit during the treatment period: (revised per Amendment 01)

- a) Immunoglobulin therapy and biologic drugs are not permitted within 6 months before Screening and until the last visit during the treatment period (revised per Amendment 01)
- b) Systemic immunosuppressive or immunomodulatory drugs are not permitted for a period of 5 half-lives or 60 days (whichever is longer) before randomization and until the last visit during the treatment period (revised per Amendments 01 and 03)
- c) Moderate to strong inhibitors of carboxylesterase 2 (CES2) enzyme activity are not permitted for a period of 5 half-lives or 7 days (whichever is longer) before randomization and until the last treatment visit. Simvastatin use is permitted only with QD evening administration.
- d) Live/live attenuated vaccines are not permitted within 3 months before randomization and until the last treatment visit (this does not apply to non-live/inactivated vaccines) (revised per Amendment 01)

Concomitant therapy with AChEI or memantine should only be allowed and/or acceptable for the region or country in which the study is being conducted and should follow the local standard of care for symptomatic treatment (revised per Amendment 01). Subjects who are taking AChEI or memantine will be required to be on a stable dose for at least 12 weeks before randomization. Initiation of therapy or changing dose of AChEIs or memantine during the study should be undertaken in compliance with local standard of care for symptomatic treatment of AD. (revised per Amendment 02). Subjects who start on AChEI or memantine

or change their dose during the Treatment Period will be permitted to continue in the study; however, subjects should not undertake cognitive assessments until they have been on a stable dose for at least 4 weeks.

Subjects who are taking other medications will be required to be on a stable dose for at least 4 weeks before randomization, except for medications which are administered as short courses (eg, up to 3 weeks unless discussed and agreed with the Medical Monitor) of treatment (eg, anti-infectives, oral steroids) or which are to be used on a PRN basis. Concomitant medications (including short-term use of benzodiazepines and opiates) which are used on a PRN basis and which are central nervous system (CNS) active and may affect cognitive function are not permitted during a period of 72 hours prior to cognitive testing. (revised per Amendment 03)

For subjects who undergo an LP for collection of CSF: Subjects who are on anticoagulants may have a variable dose but should have stable anticoagulation control for at least 4 weeks before the LP procedure. Subjects may be required to stop their anticoagulant medication prior to CSF collection and then restart this medication after the LP procedure, as per local guidelines.

Either aspirin or clopidogrel (or any other antiplatelet drug which is not aspirin) is permitted in all subjects. Aspirin and clopidogrel (or any other antiplatelet drug which is not aspirin) in combination are also permitted but subjects who are on such a combination of antiplatelet drugs may be required to stop 1 or more of these antiplatelet drugs before the LP procedure and restart after the LP as per local guidelines.

Subjects who initiate treatment with drugs not intended for treatment of cognitive impairment during the study should continue in the study if in the opinion of the investigator this will not interfere with study procedures or subject safety and are not prohibited above. However, if such drugs may affect cognitive function, subjects should not undertake cognitive assessments until they have been on a stable dose for at least 4 weeks.

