In the MAD study, AEs of interest included relapse of orolabial herpes, viral respiratory tract infection, drug rash, and abnormal dreams. More details are available in the Investigator's Brochure. In summary, elenbecestat (E2609) administered at doses of 200 and 400 mg was associated with reductions in CD4 (T helper cells), CD8 (cytotoxic T cells), and CD19 (B cells) counts at Day 8. These reductions were more clearly evident by Day 15, consistent with a treatment by time interaction in the statistical analysis. There was evidence that the lower doses of 50 to 100 mg also caused some reduction in CD4 lymphocyte counts by Day 15. Doses above 100 mg appeared to be associated with greater reductions in CD4 and CD8 lymphocyte counts, which occurred earlier in the treatment period compared with the effects of 25 to 100 mg doses. These effects on lymphocyte counts gradually resolved from Day 20 to Day 35, which were 6 and 21 days, respectively, after administration of the last dose of elenbecestat (E2609) on Day 14. Reductions in CD4 and CD8 lymphocyte counts at doses of 200 and 400 mg to a level close to or less than the lower limit of normal (LLN) could be associated with increased risk of developing relapse of orolabial herpes or other infections.

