9.3.3 Removal of Subjects from Therapy or Assessment

The investigator may withdraw the subject from the study at any time for safety or administrative reasons. The subject may stop study drug or withdraw from the study at any time for any reason.

Absolute lymphocyte count from the hematology and differential panel will be monitored during the study. ALC will be derived from the CBC with differential representing the normal lymphocytes (with atypical lymphocytes removed and presented as a separate count if they are present) and calculated by the white blood cell count \times percentage of lymphocytes. (revised per Amendment 01) Should a subject develop a Grade 2 or greater lymphocytopenia (less than $800/\text{mm}^3$), the absolute lymphocyte count test should be repeated as soon as possible with the repeat blood sample drawn no later than 5 calendar days from the date of the original test. (revised per Amendment 03) If confirmed, study drug administration should be interrupted for a minimum period of 2 weeks and for a maximum period of 4 weeks. Restart of study drug may take place only when absolute lymphocyte count returns to greater than LLN. Absolute lymphocyte count will be measured 4 weeks after restart of study drug. Subsequent measurements of absolute lymphocyte counts will follow the schedule of assessments (Table 4) and any results showing a Grade 2 or greater lymphocytopenia (less than $800/\text{mm}^3$) should be handled as above. If a 2nd occurrence of Grade 2 or greater lymphocytopenia (less than $800/\text{mm}^3$), that is confirmed on repeat testing, occurs within 6 months, then the subject should be discontinued permanently from the study drug.

Subjects who develop moderate or severe hepatic impairment (eg, Child-Pugh Class B or C) during the study must discontinue study drug. (revised per Amendments 01 and 02) Moderate or severe hepatic impairment are defined as any 2 of the following criteria: $\text{INR} \geq 1.7$; bilirubin $\geq 1.5 \times \text{ULN}$; albumin $< \text{LLN}$; ascites or hepatic encephalopathy. Please note that a single significant abnormality could meet criteria for moderate impairment. (revised per Amendment 02)

Subjects who develop seizures will be discontinued from study drug. (revised per Amendment 02)

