Immune globulin IV, IVIG, IGIV	Carimune, Flebogamma, Gamimune N, Gammagard, Gamunex, Gammar-P IV, Iveegam, Octagam, Panglobulin, Vigam, Polygam S/D, Privigen, Sandoglobulin, Venoglobulin-S
Denosumab	Prolia (revised per Amendment 01)
Other monoclonal antibodies not listed here	

^aTopical, ocular, and inhaled formulations with minimal systemic exposure need not be prohibited. (revised per Amendment 03)

Listing 3 Prohibited Live/Live Attenuated Vaccines Within 3 Months Before Randomization and Until the Last Visit During the Treatment Period (this does not apply to non-live/inactivated vaccines)

Bacterial vaccines	Viral vaccines
Bacillus Calmette-Guérin vaccine against tuberculosis	Measles vaccination
Typhoid vaccination (oral)	Mumps vaccination
Cholera vaccination (oral)	Rubella vaccination
	Oral polio vaccination (Sabin)
	Yellow fever vaccination
	Varicella (chickenpox) vaccination
	Rotavirus vaccination
	Japanese encephalitis vaccination
	Live attenuated influenza vaccine (FluMist in the United States and Canada, and Fluenz in Europe)

This list is not exhaustive

Permitted Prior/Concomitant Medications

Listing 4 Medications Which Need To Be on a Stable Dose for 12 Weeks Before the Cognitive Assessments at Visit 2 and Should Remain on the Same Stable Dose From Visit 2 to Follow Up Visit 15

Cognitive Enhancers	
Donepezil	Aricept
Rivastigmine	Exelon
Galantamine	Reminyl
Memantine	Namenda

Listing 5 Permitted Medications Used on PRN Basis Which Are Not to be Used Within 72 Hours Before Cognitive Testing

Generic name	Trade name
Opiates	
Morphine	Astramorph PF, Avinza, Depo Dur, Duramorph, Infumorph, Kadian, MS Contin, MSIR, Oramorph SR, RMS, Roxanol
Opiate Agonists	
Meperidine	Demerol, Meperitab
Fentanyl	Actiq, Duragesic, Fentora, Onsolis, Sublimaze
Codeine	Codeine
Oxycodone	Dazidox, Endocodone, Eth-OxyDose, OxyContin, OxyFast, OxyIR, Percolone, Roxicodone, Roxicodone Intensol
Other opioids or opioid agonists which are used on PRN basis	
Benzodiazepines (short-term use only, [ie, 2 to 4 weeks]) and sedatives (revised per Amendment 03)	
Estazolam	ProSom
Alprazolam	Alprazolam Intensol, Niravam, Xanax
Triazolam	Halcion
Midazolam	Versed
Lorazepam	Ativan
Flunitrazepam	Rohypnol
Temazepam	Restoril
Clonazepam	Ceberclon, Klonopin
Diazepam	Diastat, Dizac, Valium
Chlordiazepoxide	H-Tran, Librium
Flurazepam	Dalmane
Zopiclone	(various)
Zolpidem	Ambien; others
Ramelteon	Rozerem
Amitriptyline	(various)
Dothiepin	(various)
Risperidone	Risperdal
Olanzapine	Zyprexa

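### The live-vaccine ban ends at the last treatment visit, a dosing day for completers, with no period off drug and no lymphocyte condition

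*Protocol*

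**What the plan says.** Section 9.4.7(d): "Live/live attenuated vaccines are not permitted within 3 months before randomization and until the last treatment visit". Appendix 2 Listing 3 carries the heading "Prohibited Live/Live Attenuated Vaccines Within 3 Months Before Randomization and Until the Last Visit During the Treatment Period". The two agree. Neither adds time after the last dose or refers to a lymphocyte count. Inactivated vaccines are outside the ban.

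The protocol's evidence on lymphocytes is in Section 7.1, in the account of the MAD study (Study 002: healthy subjects aged 50 to 85, 14 days of dosing). At the lower doses: "There was evidence that the lower doses of 50 to 100 mg also caused some reduction in CD4 lymphocyte counts by Day 15". On recovery: "These effects on lymphocyte counts gradually resolved from Day 20 to Day 35, which were 6 and 21 days, respectively", counted from a last dose on Day 14. The sentence linking low counts to herpes relapse or other infection is about "Reductions in CD4 and CD8 lymphocyte counts at doses of 200 and 400 mg".

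Section 9.3.3 governs a confirmed ALC below 800/mm3 on treatment. At a first episode, "study drug administration should be interrupted for a minimum period of 2 weeks and for a maximum period of 4 weeks", and "Restart of study drug may take place only when absolute lymphocyte count returns to greater than LLN". For a second episode "that is confirmed on repeat testing, occurs within 6 months, then the subject should be discontinued permanently from the study drug".

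**The concern.** The protocol bans live vaccines for the whole time a subject takes 50 mg a day. It then lifts the ban at a visit where a completer has just taken a dose. Pharmacologically that subject is still on treatment, so whatever justified the ban the day before still holds. The protocol's only information on recovery describes effects that took up to 21 days off drug to resolve.

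The second difficulty is the missing lymphocyte condition. Other decisions depend on the count: eligibility (Section 9.3.2, criterion 9), restart after an interruption (Section 9.3.3) and repeat testing in follow-up (Section 9.5.1.5.1). The release from the live-vaccine ban does not. A subject taken off drug for good because of low lymphocytes is released on the same terms as anyone else. At stake is a live vaccine given before a drug effect on lymphocytes has cleared.

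**Working it through.** **Inputs**
- Last dose in the MAD study: Day 14; resolution described from Day 20 to Day 35 (Section 7.1).
- Visit 13 is Day 729 and Visit 14 is Day 757 (Table 4). Follow-Up Visits have a window of ±3 days (Table 4, footnote a).
- Dosing in clinic at Visit 13 (Section 9.5.1.4.1).
- ED visit within 7 days of the last dose (Table 4, footnote b).

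**The protocol's own figures.** 20 − 14 = 6 days and 35 − 14 = 21 days. Both are reproduced.

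**Cover given by the present rule.** A completer takes a dose at Visit 13 and the ban ends at Visit 13, so it covers 0 days off drug. For an early discontinuer the protocol does not say which visit is the last treatment visit. Read as the ED visit, the cover is 0 to 7 days when no interruption came before the stop.

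**Hypothetical gap.** Suppose the MAD end point of 21 days applied at 50 mg after 24 months, which the protocol does not say. With d days off drug at release, the gap is max(0, 21 − d):

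| Subject | d (days) | Gap (days) |
|---|---|---|
| Completer | 0 | 21 |
| ED visit, no prior interruption | 0 to 7 | 14 to 21 |
| Stopped after a 14-day interruption | 14 | 7 |
| Stopped after an interruption of 21 days or more | ≥ 21 | 0 |

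The range of 0 to 21 days only shows scale. The true figure at 50 mg could be shorter or longer.

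**The ALC route, which does not need the 21 days.** A second confirmed ALC below 800/mm3 within 6 months ends study drug permanently. Section 9.4.7(d) then releases the subject at the ED visit (same reading as above) whatever the ALC is that day.

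**What existing procedures do.** Hematology is drawn at the ED visit and at Visits 14 and 15 (Table 4). ALC below 800/mm3 at Visit 14 or 15 leads to testing every 4 weeks (Section 9.5.1.5.1). Under Section 9.5.7 subjects tell the site about planned outside care and the investigator, with consent, notifies the other physician of trial participation. All of these inform someone. None bars a live vaccine.

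**Cover under the proposed rule.** Visit 14 falls 757 − 729 = 28 days after the last dose for completers, or 25 to 31 days with the window. The earliest Visit 14 is 25 − 21 = 4 days beyond the MAD end point.

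**The case against.** The best case for leaving the text alone is that the end point was chosen on purpose. All four bans in Section 9.4.7 end at the last treatment visit, and the revision history shows that Amendment 01 set that time frame and added live vaccines to the list. The evidence also sits away from this trial: the lymphocyte reductions were clearest at 200 and 400 mg, the infection warning is tied to those doses, the measurements were cell subsets rather than ALC, and dosing lasted 14 days. Sites will know which subjects have low counts, and Section 9.5.7 gives other physicians advance notice.

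Most of this stands, and it keeps the point small. It does not remove it. The rationale recorded for the Amendment 01 change is clarification; no reason is given against a period off drug. The protocol already treats live vaccines as unsuitable at 50 mg, and nothing in it suggests that the reason ends on the day of the last dose.

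Three stronger readings are tempting and not supported:
- A reader might take the 21 days as a finding across Phase 1. It comes from the MAD study alone; the single-dose lymphocyte results are reported separately in Section 7.1 as inconclusive.
- A reader might infer that subjects whose first episode has not recovered at the 4-week interruption limit are also released. Section 9.3.3 sets the limit and the restart condition but does not state that they are discontinued, although it does say so for severe infection, rash and herpes. While drug is only interrupted, the ban still applies.
- A reader might see a contradiction. Section 9.4.7(d) and Listing 3 agree; this is a design choice.

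**Conclusion.** The point holds as a minor, optional safety improvement. It is certain that the ban ends on a dosing day for completers and has no ALC condition. That this leaves subjects exposed for a particular number of days is not established: the 0 to 21 days carry the MAD end point over to a lower dose and a much longer exposure. The release of subjects stopped for a second low count is independent of that figure, but rests on reading the ED visit as the last treatment visit. The protocol gives no basis for estimating how many subjects would receive a live vaccine in this period.

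**What to change.** In Section 9.4.7(d) and the heading of Listing 3, continue the live-vaccine ban until Visit 14, or until 28 days after the last dose if Visit 14 is missed. Add that if ALC is below 800/mm3 at Visit 14 or 15, the subject is advised to defer live vaccines until the count resolves or a cause other than the drug is confirmed, as in the ALC follow-up rule of Section 9.5.1.5.1. This second part is advice because it can run past Visit 15. Leave the other bans as they are; extending the one on systemic immunosuppressants could obstruct needed treatment such as steroids for a rash.

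The cost is one or two sentences in the next amendment, with no new visits or tests. Live vaccination is deferred by about 4 weeks, in placebo subjects as well. Two limits remain: ALC is not a CD4 or CD8 count, and subjects with ALC between 800/mm3 and the lower limit of normal are not held beyond Visit 14.

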9.4.7.1 Drug-Drug Interactions

Listings of prohibited drugs are provided in [Listing 1](#), [Listing 2](#), and [Listing 3](#).

9.4.8 Treatment Compliance

Records of treatment compliance for each subject will be kept during the Treatment Period of the study. CRAs will review treatment compliance during site visits and at the completion of the study.

9.4.9 Drug Supplies and Accountability

In compliance with local regulatory requirements, drug supplies will not be sent to the investigator (or if regionally required, the head of the medical institution or the designated pharmacist) until the following documentation has been received by the sponsor:

- A signed and dated confidentiality agreement

- A copy of the final protocol signature page, signed and dated by both the sponsor and investigator
- Written proof of approval of the protocol, the ICFs, and any other information provided to the subjects by the IRB/IEC for the institution where the study is to be conducted
- A copy of the IRB/IEC-approved ICF and any other documentation provided to the subjects to be used in this study
- The IRB/IEC membership list and statutes or Health and Human Services Assurance number
- A copy of the certification and a table of the normal laboratory ranges for the reference laboratory conducting the clinical laboratory tests required by this protocol
- An investigator-signed and dated Food and Drug Administration (FDA) Form FDA 1572, where applicable
- Financial Disclosure form(s) for the principal investigator and all subinvestigators listed on Form FDA 1572, where applicable
- Current medical license or proof of qualification of principal investigator (not required for sites outside North America if the qualification can be verified by their curriculum vitae) (revised per Amendment 01)
- A signed and dated Clinical Trial Agreement (CTA)
- A copy of the regulatory authority approval for the country in which the study is being conducted (if required), and the Import License (if required)

The investigator and the study staff (or if regionally required, the head of the medical institution or the designated pharmacist) will be responsible for the accountability of all study drugs (dispensing, inventory, and record keeping) following the sponsor's instructions and adherence to GCP guidelines as well as local or regional requirements.

Under no circumstances will the investigator allow the study drugs to be used other than as directed by this protocol. Study drugs will not be dispensed to any individual who is not enrolled in the study.

The site must maintain an accurate and timely record of the following: receipt of all study drugs, dispensing of study drugs to the subject, collection and reconciliation of unused study drugs that are either returned by the subjects or shipped to site but not dispensed to subjects, and return of reconciled study drugs to the sponsor or (where applicable) destruction of reconciled study drugs at the site. This includes, but may not be limited to: (a) documentation of receipt of study drugs, (b) study drugs dispensing/return reconciliation log, (c) study drugs accountability log, (d) all shipping service receipts, and (e) documentation of returns to the sponsor. All forms will be provided by the sponsor. Any comparable forms that the site wishes to use must be approved by the sponsor.

The study drugs and inventory records must be made available, upon request, for inspection by a designated representative of the sponsor or a representative of a health authority (eg, FDA, Medicines and Healthcare Regulatory Agency). As applicable, all unused study

drugs and empty and partially empty containers from used study drugs are to be returned to the investigator (or if regionally required, the head of the medical institution or the designated pharmacist) by the subject and, together with unused study drugs that were shipped to the site but not dispensed to subjects, are to be returned to the sponsor's designated central or local depot(s) during the study or at the conclusion of the study, unless provision is made by the sponsor for destruction of study drugs and containers at the site. Destruction at the site will only occur under circumstances where regulation or supply type prohibits the return of study drugs to the central or local depot(s). Approval for destruction to occur at the site must be provided by the sponsor in advance. Upon completion of drug accountability and reconciliation procedures by the site's personnel and documentation procedures by the sponsor's personnel, study drugs that are to be returned to the sponsor's designated central or local depot(s) must be boxed, sealed, and shipped back to the central or local depot(s) following all local regulatory requirements. In some regions, study drugs may be removed from the site and hand delivered to the central or local depot by sponsor representatives. Where study drugs are approved for destruction at the site, destruction will occur following the site's standard procedures and certificates of destruction will be provided to the sponsor.

Drug accountability will be reviewed during site visits and at the completion of the study.

